5.2. Exclusion Criteria

- The participant may not enter the study if they have any contraindication to magnetic resonance imaging (standard MR exclusion criteria including pregnancy, extensive tattoos, pacemaker, shrapnel injury, severe claustrophobia).
- Patients with known autoimmune hepatitis, viral hepatitis, Wilson's disease, haemoglobinopathies or significant structural renal tract abnormality.
- Patients with known excessive alcohol intake.
- Any other cause, including a significant disease or disorder which, in the opinion of the investigator, may either put the participant at risk because of participation in the study, or may influence the participant's ability to participate in the study.

6. Sample size

The primary endpoint of the study is to compare the MRI metrics for liver fibroinflammation in those patients with type 2 diabetes at baseline vs. individuals who are healthy and non-diabetic. Values for the healthy, non-diabetics will be provided from data from the UK Biobank (UKBB)(30) or from other studies (31). Healthy individuals will be matched to the diabetic population based on gender, age and ethnicity. Analysis will be based on a two-sample, two-sided t-test.

The sample size required to perform a t-test with 90% power and alpha of 0.05 would require n=150. Based on MRI metric for liver fibroinflammation (cT1) this assumes:

- Detection of a 24.87 ms difference in cT1 in liver (This represents 50% of the difference in cT1 between self-reported diabetes vs healthy subgroups within the UK Biobank), based on unpublished data from Perspectum)
- SD of 42ms (pooled SD from self-reported diabetes and healthy subgroups within UKBB, based on unpublished data from Perspectum)
- 20% drop-out rate.

Secondary endpoints of the study include separate comparisons of MRI metrics for liver fat infiltration and volume in patients with type 2 diabetes vs. the same metrics in healthy, non-diabetic individuals. Values for the healthy, non-

diabetics will be provided from data from the UK Biobank (30) or or from other studies (31) and will be selected based on the matching of gender, age, ethnicity to the patients from this study with type 2 diabetes. Analysis will be based on two-sample, two-sided t-tests.

Based on MRI metric for liver fat infiltration (PDFF), the sample size required to perform the t-test with 90% power and alpha of 0.05 would require n=150. This assumes:

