- Detection of a 2.4% difference in PDFF [This represents 63% of the difference in PDFF between self-reported diabetes vs healthy subgroups within UK Biobank, unpublished Perspectum]
- Measurement SD of 5.4% (Pooled SD from self-reported diabetes and healthy subgroups within UK Biobank, based on unpublished data from Perspectum)
- 20% drop-out rate.

Based on MRI metric for liver volume, the sample size required to perform the t-test with 90% power and alpha of 0.05 would require n=150. This assumes:

- Detection of a 0.084 L difference in liver volume in liver (This represents 6% of the pooled mean from UK Biobank data, unpublished Perspectum)
- Measurement SD of 0.289 L (pooled mean from UK Biobank data, unpublished Perspectum)
- 20% drop-out rate.

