7.3.1. Standard study visit – assessments

Medical history (~10 min)

We will obtain a full medical history including age, diabetes presentation, diabetes complications, diabetes duration, previous and current diabetes medication, current medication regime, family history, smoking history, alcohol history, ethnicity, history of cardiovascular disease, QRISK score, history of kidney disease, history of liver disease and record of any other co-morbidities the patient may have.

We will confirm that the participant has no contraindications for MRI (e.g. pregnancy, pacemaker or other metallic unfixed implanted device, metallic fragments, extensive tattoos, severe claustrophobia, metal in clothing). A resting blood pressure measurement will be taken.

All measurements will be recorded on the study participant’s Case Report Form (CRF).

Anthropometric measurements (5 min)

We will measure the height and weight of the participant to calculate BMI and also take hip and waist circumference.

Blood sample (10 min)

Routine bloods will be performed as per standard-of-care for T2D or its complications and will include: HbA1c, serum creatinine, electrolytes, lipids, FBC (full blood count), LFT (liver function tests that include aspartate transaminase and alanine transaminase) and gamma glutamyl transferase (GGT). eGFR will also be calculated.

A further blood sample of approximately 10 ml will be taken to measure additional circulating biomarkers [such as the enhanced liver fibrosis test (ELF), N-terminal levels of type III procollagen (P3NP), pancreatic lipase, cystatin C, serum albumin, high sensitivity C-reactive protein, NT-proBNP and uric acid] and optional genetic testing for NAFLD or T2D associated genetic variants. Consent for genetic testing and to place blood samples in the biobank at Liverpool, Royal Free London or Oxford for future testing will be optional for all participants for up to 7 years after baseline to enable evaluation after full study completion.

Biomarker	Key organ(s)
HbA1c	Various/pancreas
Lipids	Various
GGT	Liver (various)

Full Blood Count	Various
LFT, including AST and ALT	Liver
Serum Creatinine	Kidney
Urine Albumin Creatinine Ratio	Kidney
Electrolytes	Kidney

Table 2 - Standard of care circulating biomarkers in study

Urine sample (10 min)

Routine urine sample collection will be performed as per standard of care to measure urine dipstick and urine albumin creatinine ratio.

MRI Scan (~30min)

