10.2. Analysis plan

Descriptive statistics will be used to summarise subject characteristics. Summary data will be calculated for MRI metric values (Table 3). Normality will be determined by use of the Shapiro-Wilk test. Results will be expressed as means with standard deviation (SD) for continuous variables and as numbers and percentages for categorical variables.

Analysis of variance will be used to test for differences between multiple groups.

The primary endpoint will be a comparison of MRI metric values for fibro-inflammation in the liver compared to a matched non-diabetic control group from the UK Biobank(30) or from other studies (31) (Table 3). This will be assessed with a two-sample, two-sided t-test. Secondary endpoints include a comparison of individual MRI metric values [summarised in table 3 below] in individual organ associated with T2D and its comorbidities [summarised in table 3 below] at baseline (visit 1/visit 2) compared to a matched non-diabetic control group from the UK Biobank or other studies. These will also be assessed with two sample, two-sided t-tests. Additionally, the prevalence of mean liver PDFF and / or mean liver cT1 above NAFLD thresholds in the study cohort will be compared to the matched non-diabetic control group, using a Chi-squared test.

MRI metric	Organ(s) or Location(s)	Associated organ characteristic
For primary endpoint		
cT1	Liver	Fibro-Inflammation
For secondary endpoints		
Diameter of Aorta	Heart	Local Blood Flow
Aortic Distensibility	Heart	Elasticity of Aorta
T1	Spleen, Kidney, Pancreas	Fibro-Inflammation
T2*	Spleen	Iron Level
PDFF	Liver, Spleen, Pancreas	Fat content
Volume	Liver, Spleen, Kidney, Pancreas	Size
Optional exploratory endpoint metrics		
T2* Gradient	Kidney	Oxygenation
D	Kidney	Glomerular Filtration
PDFF	Kidney	Fat Content

Volume of Visceral Adipose Tissue (VAT)	Abdomen	Fat Content
Abdominal Subcutaneous Adipose Tissue Volume (ASAT)	Abdomen	Fat Content
Skeletal Muscle Index	Abdomen	Muscle Content

Table 3 - MRI metrics in relevant organs

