Change from baseline in MRI metrics values at 6 to 9-months post-treatment will be assessed as secondary endpoints in each organ. These will be assessed with linear mixed effects model with an interaction variable of time. The change from baseline in proportion of patients at 6 to 9 months with mean PDFF and / or mean cT1 above NAFLD thresholds, across the whole study cohort, will be assessed using Chi-squared tests. Equivalent changes from baseline at 6 to 9 months will be assessed for HbA1c (glycaemic control), and other circulating biomarkers utilised in the clinical pathway for T2D, NASH and CKD [serum creatinine and eGFR (kidney), urine albumin creatinine ratio (kidney), lipids (NALFD), LFT (liver)], using linear mixed effects to assess changes over time. Odds ratios will be calculated by logistic regression analysis in relation to cardiovascular, liver, pancreatic and kidney-related events and or death, including hospital admissions, at 1, 3 and 5 years from baseline.

Exploratory endpoints will investigate the potential influence of glycaemic control/weight and of glucose/lowering therapies (oral/injectable agents) on prevalence of abnormality based on thresholds set from the healthy controls and on rate of progression for both biochemical and MRI-metrics, in subgroup analyses (including subgroups with abnormalities in multiple organs). Multiple testing will be corrected with Bonferroni correction. In addition, analysis of covariance will provide estimates of MRI metrics, adjusting for potential confounders such as baseline MRI metric, type of co-morbidity, type of therapeutic, HbA1c values, anthropometric measures and organ-specific circulating biomarker values as covariates. Similarly, additional associations of MRI metrics to biomarkers that are optional [for example left ventricular strain from the ECHO] or not in standard of care [for example pancreatic lipase] may be analysed, if evaluated locally or from stored, consented additional blood samples. Thresholds will be set based on Kaplan–Meier analysis to establish the proportions of patients in different MRI metric categories that remain free of diabetes-related events in the follow-up period. Differences between the curves will be compared using the log-rank test.

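### External controls are matched on gender, age and ethnicity, but the continuous baseline comparisons are fixed as unadjusted t-tests; adjusting for the same three factors would recover precision at almost no cost

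*Protocol*

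**What the plan says.** Section 6 (Sample size) takes healthy, non-diabetic values from UK Biobank or other studies and states for the primary endpoint: "Healthy individuals will be matched to the diabetic population based on gender, age and ethnicity. Analysis will be based on a two-sample, two-sided t-test". For liver fat and liver volume, the control values "will be selected based on the matching of gender, age, ethnicity to the patients from this study with type 2 diabetes", again with two-sample t-tests.

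Section 10.2 (Analysis plan) repeats the two-sample, two-sided t-test for liver cT1. Of the other continuous baseline comparisons it says: "These will also be assessed with two sample, two-sided t-tests". NAFLD prevalence is compared with a Chi-squared test.

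The only covariate-adjusted analysis is an analysis of covariance in the exploratory paragraph of Section 10.2, "adjusting for potential confounders such as baseline MRI metric, type of co-morbidity, type of therapeutic, HbA1c values, anthropometric measures and organ-specific circulating biomarker values". The list is open, but it does not name gender, age or ethnicity. Some of its items, such as type of therapeutic, have no counterpart in a healthy control.

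**The concern.** Matching on factors that predict the outcome makes the two groups alike on those factors, so the group difference varies less from sample to sample. A two-sample t-test treats the groups as independent, unmatched samples and does not credit that reduction. Its standard error is too large, its confidence interval too wide, and its true type I error below 5%. The design does the work of matching and the analysis gives up the benefit.

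Matching to an external source may also be imperfect. Any residual imbalance in age, sex or ethnicity stays in an unadjusted difference, whereas a regression on the same factors largely takes it out where the groups overlap. At stake are the width of the interval for the T2D-versus-healthy difference and the power of comparisons with little to spare.

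**Working it through.** **Inputs from Section 6.** Two-sided alpha 0.05; power 90%; 20% drop-out; n=150 for each metric. cT1: difference 24.87 ms, SD 42 ms. PDFF: 2.4 with SD 5.4 (percentage points). Liver volume: 0.084 L ("Detection of a 0.084 L difference in liver volume in liver") with "Measurement SD of 0.289 L".

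**Assumptions, not in the documents.** R² is the share of within-group variance explained by gender, age and ethnicity, taken from 0.02 to 0.30. The main case has 120 patients (150 × 0.8) and 120 controls. The alternative has 60 per group, for the reason given in step 1.

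**1. The plan's own figure.** The protocol says: "The sample size required to perform a t-test with 90% power and alpha of 0.05 would require n=150". For cT1, n per group = 2 × (1.960 + 1.282)² × (42/24.87)² = 59.9, so 60. Two groups make 120, and 120/0.8 = 150. The stated figure therefore reproduces as a total over two equal groups, although the protocol recruits 150 patients. Hence both 60 and 120 per group are shown.

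**2. The t-test after close matching.** The nominal standard error is SD × √(2/n), but the true one is SD × √(2/n) × √(1−R²). The true type I error is P(|Z| > 1.96/√(1−R²)):

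- R² 0.05: 0.044
- R² 0.10: 0.039
- R² 0.30: 0.019

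The test is conservative, not invalid. Simulated matched pairs agreed (0.036 to 0.044 at R² 0.10; 0.019 at R² 0.30).

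**3. Adjusted analysis.** The standard error becomes SD × √(1−R²) × √(2/n). The factor √(1−R²) is 0.990, 0.975, 0.949 and 0.837 at R² 0.02, 0.05, 0.10 and 0.30. It is the same for every metric at equal R². For cT1 at 120 per group, the unadjusted standard error is 42 × √(2/120) = 5.42 ms, and the half-width is 1.96 × 5.42 = 10.63 ms.

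Normal approximation; the row R² = 0 is the unadjusted planning formula:

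| R² | cT1 half-width, 120/group (ms) | cT1 power, 120/group | PDFF power, 120/group | Liver-volume power, 120/group | cT1 power, 60/group |
|---|---|---|---|---|---|
| 0 | 10.63 | 99.6% | 93.1% | 61.5% | 90.0% |
| 0.02 | 10.52 | 99.6% | 93.5% | 62.3% | 90.6% |
| 0.05 | 10.36 | 99.7% | 94.2% | 63.7% | 91.4% |
| 0.10 | 10.08 | 99.8% | 95.2% | 66.0% | 92.8% |
| 0.30 | 8.89 | >99.9% | 98.4% | 76.8% | 97.2% |

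Close matching by itself lifts the power of the t-test a little. At R² 0.10 and 0.30, liver volume at 120 per group reaches 62.1% and 63.6%, and cT1 at 60 per group 91.2% and 93.7%. The gain due to adjustment is the remainder.

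**4. Limits of the gain.** At 120 v 120, liver volume reaches 90% power only if R² is at least 1 − [0.084 / (3.242 × 0.289 × √(2/120))]² = 0.52. With no adjustment, 120 patients against a very large control set give about 89%. The unstated control ratio can therefore matter more than the covariates.

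**5. Cost in precision.** Three covariate terms inflate the variance by about 1% at 120 per group and 2.6% at 60 per group. At R² near 0.02 and 60 per group, the net gain is therefore nil.

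**The case against.** The strongest reply is that nothing is wrong with the inference. Matching followed by a simple test is a recognised approach, it errs on the safe side, and cT1 power at 120 per group exceeds 99%. That stands: this is a point about efficiency, not a flaw that threatens the primary conclusion.

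The size of the gain also rests on an R² that the documents do not give. With R² near zero there is almost nothing to win. That stands too, and is why the range starts at 0.02. The benefit against residual imbalance is likewise conditional, because the documents do not say how close the matching will be.

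A reader might infer that the gain is largest for liver volume. As a claim about precision, this is unsupported: at equal R² the proportional gain is the same for every metric, and no metric-specific R² is given. As a claim about power, it depends on the group size. At R² 0.10 and 120 per group, liver volume gains 4.6 points, PDFF 2.1 and cT1 0.2. At 60 per group, PDFF gains most (68.2% to 72.8%, against 35.7% to 38.9% for liver volume). The low liver-volume power is itself a sample-size matter: its inputs need 249 per group before drop-out.

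The exploratory analysis of covariance has an open list and could include the three factors. It does not govern the primary or secondary comparisons, for which Sections 6 and 10.2 name the t-test.

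Finally, the protocol is at version 9.0 and recruitment has begun, so a change of primary model could look data-driven. This bears on how the change is documented. It does not remove the gain.

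**Conclusion.** The point holds as a low-cost improvement. The protocol matches on three factors and then fixes a test that ignores them, with no adjustment for them named elsewhere. The t-test is valid but conservative under close matching.

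Over the assumed range of R², adjustment shortens the intervals by 1% to 16%, before the small loss for fitting the covariates. For cT1 at 120 per group the effect on power is negligible; at 60 per group, power moves from 90% to between 91% and 97%. The gains for PDFF and liver volume are those in the table.

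Three stronger readings are not supported: that the primary result is at risk, that adjustment rescues the liver-volume sample size at 1:1, and that it removes differences due to the control source. All magnitudes depend on an R² and a number of controls that the documents do not state.

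**What to change.** In Sections 6 and 10.2, make the primary comparison and the continuous baseline secondary comparisons a linear regression of the metric on group (T2D v control), with age, sex and ethnicity in broad categories as covariates. Report the adjusted difference with its 95% confidence interval, and keep the two-sample t-test as a supporting analysis. The Chi-squared test for NAFLD prevalence can stay. Date the change before the comparison with controls is run, so that it cannot be read as data-driven.

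The cost is a wording change with that dated record, and a few degrees of freedom. No new data are needed: Section 7.3.1 collects patients' age and ethnicity ("family history, smoking history, alcohol history, ethnicity, history of cardiovascular disease"), and matching already requires all three factors in both groups.

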2. INTRODUCTION

2.1. Background and Rationale

There has been a surge in incidence of the metabolic syndrome; a cluster of conditions which increase the risk of:

- type 2 diabetes (T2D) (90% of diabetes cases),
- non-alcoholic fatty liver disease (NAFLD),
- non-alcoholic steatohepatitis (NASH),
- cardiovascular disease (including ischaemic heart disease and heart failure),
- ischaemic or haemorrhagic stroke

This project concentrates on T2D, a disease whose multiple pathophysiological defects include:

- increased renal glucose reabsorption,
- decreased peripheral glucose utilisation,
- increased hepatic glucose production due to insulin resistance,
- increased glucagon secretion,
- reduced insulin secretion (pancreas),
- and incretin secretion (gastrointestinal tract)

Estimated UK prevalence of T2D is 5.26%. This represents 3.3 million people (1) (comparatively in the US, 9.1% or 26.44 million people (2)), which equates to £8.8bn in associated healthcare costs in UK (3).

Type 2 diabetes is associated with a heterogeneity in its aetiology – this is observed in its clinical presentation and subsequent rate of progression. Further factors associated with T2D include micro- and macrovascular complications and an observed decline in multiple organs (end-organ damage). End-organ damage contributes to the clinical picture of individuals with T2D and is demonstrated when observing the high prevalence of co-morbidities in this patient cohort. For example, the presence of NAFLD is seen in 60% of T2D patients (4, 5), along with a 34.2-50.7% presence of chronic kidney disease (CKD)(6) and a 32.2% presence of cardiovascular disease (CVD)(7).

Currently, T2D and its complications are monitored using circulating plasma and serum biomarkers (8). However, these lack sufficient sensitivity or specificity. An example of this is highlighted in one researcher's preliminary data that suggests that 85% of obese people with T2D had NAFLD, detected by MRI. However, a vast proportion of this patient cohort have recorded normal biochemical biomarkers, such as Alanine Transaminase (ALT).

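### The patient-control comparisons of organ volume and aortic diameter specify no matching, indexing or adjustment for body size, so a raw size difference cannot by itself be read as organ abnormality

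*Protocol*

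**What the plan says.** Section 6 takes the healthy, non-diabetic values from UK Biobank or other studies and fixes the matching set for the primary endpoint: "Healthy individuals will be matched to the diabetic population based on gender, age and ethnicity". For liver fat and liver volume it repeats the same three factors; control values "will be selected based on the matching of gender, age, ethnicity to the patients from this study with type 2 diabetes".

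The planned liver-volume effect is in raw litres: "Detection of a 0.084 L difference in liver volume in liver (This represents 6% of the pooled mean from UK Biobank data". Table 3 in Section 10.2 lists plain volume for liver, spleen, kidney and pancreas, and plain aortic diameter. Muscle, among the optional exploratory metrics, is the only entry named as an index.

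The test is also fixed. For the primary endpoint Section 10.2 says "This will be assessed with a two-sample, two-sided t-test", and for the secondary baseline metrics "These will also be assessed with two sample, two-sided t-tests".

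Body size appears in three other places:

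- Section 7.3.1, for patients: "We will measure the height and weight of the participant to calculate BMI and also take hip and waist circumference".
- Section 10.2, exploratory paragraph: the influence of weight on prevalence of abnormality and on progression is examined in subgroups, and an analysis of covariance lists anthropometric measures among potential confounders.
- Section 10.2, last paragraph: correlations between MRI metrics and weight are given as an example.

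**The concern.** Liver, spleen, kidney and pancreas volumes and aortic diameter can be expected to vary with body size. Matching on gender, age and ethnicity removes some of that variation, since gender carries part of the height difference, but it does not balance weight. The protocol itself treats anthropometric measures as potential confounders, yet leaves them out of the comparisons on which the secondary claims rest.

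What is at stake is interpretation. Secondary objectives 1 and 2 ask for the degree of abnormality in the liver and in the other organs. A significant difference in raw volume or diameter would naturally be reported as such an abnormality. If the groups differ in body size, some or all of that difference may be larger organs in larger bodies. The exploratory prevalence analyses take their thresholds from the same healthy controls, so any size metric used there would carry the same ambiguity.

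Matching set, metric and test are all stated in the protocol. This is therefore not a gap that a later analysis plan would simply fill.

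**Working it through.** **Inputs from the protocol (Section 6).** Liver-volume difference 0.084 L, stated as 6% of the pooled mean; SD 0.289 L; two-sided alpha 0.05; power 90%; drop-out 20%; n = 150. For cT1: 24.87 ms, stated as 50% of the UK Biobank gap; SD 42 ms.

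**The plan's own figures.** Implied mean liver volume: 0.084 / 0.06 = 1.40 L. For cT1 the usual formula gives 60 per group, and 60 / 0.8 = 75 per group, or 150 as a two-group total. For liver volume, n per group = 2 × [(1.960 + 1.282) × 0.289 / 0.084]² = 249, and 249 / 0.8 = 312, so 150 does not reproduce at one control per patient. With 150 × 0.8 = 120 evaluable patients, power for 0.084 L is 61% at one control per patient and 88% at fifty. The protocol states no number of controls.

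**Inputs the protocol does not give (assumptions).** A BMI gap of 3 kg/m2; a correlation r between liver volume and BMI of 0.2 to 0.6; a BMI SD of 4 to 6 kg/m2.

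**Formulas.** Slope = r × 0.289 / SD(BMI). Body-size component = gap × slope. Gap that would produce the planned difference = 0.084 / slope.

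| r | SD(BMI) | slope, L per kg/m2 | 3 kg/m2 gives | gap for 0.084 L |
|---|---|---|---|---|
| 0.2 | 6 | 0.0096 | 0.029 L | 8.7 kg/m2 |
| 0.2 | 4 | 0.0144 | 0.043 L | 5.8 kg/m2 |
| 0.4 | 5 | 0.0231 | 0.069 L | 3.6 kg/m2 |
| 0.6 | 6 | 0.0289 | 0.087 L | 2.9 kg/m2 |
| 0.6 | 4 | 0.0433 | 0.130 L | 1.9 kg/m2 |

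For 3 kg/m2 to give 0.084 L, the slope must be 0.084 / 3 = 0.028 L per kg/m2, or 2.0% of the 1.40 L mean. That requires r = 0.028 × SD(BMI) / 0.289: 0.39 at an SD of 4 and 0.58 at an SD of 6.

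**Cross-check by a second route.** Assume equal height, so that body surface area goes with the square root of BMI, and volume proportional to surface area. BMI 27 against 30 then gives 1.40 × (√(30/27) − 1) = 0.076 L. If volume follows only the square root of surface area, the same pair gives 0.037 L. Both lie inside the range above.

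**How often the raw test would be significant.** Suppose the difference at equal body size is zero and there are 120 per group (the control number is an assumption). A body-size component of 0.03 L gives p < 0.05 in 13% of studies, and 0.084 L in 61%.

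**cT1, for comparison.** With SD 42 ms, an assumed BMI SD of 4.5 and r of 0.1 to 0.5, a 3 kg/m2 gap gives 3 × r × 42 / 4.5 = 2.8 to 14.0 ms. The full UK Biobank gap is 24.87 / 0.5 = 49.74 ms. Even the upper value leaves 49.74 − 14.0 = 35.7 ms, above the planned 24.87 ms.

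**Other size metrics.** The protocol gives no mean or SD for spleen, kidney or pancreas volume or for aortic diameter, so no figure can be computed for them.

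**The case against.** The strongest reply is that the plan does not ignore body size. Section 10.2 provides for an analysis of covariance with an open list of confounders that includes anthropometric measures, examines the influence of weight on abnormality defined from the controls, and correlates MRI metrics with weight. This stands to the extent that it would be wrong to say the plan contains no adjustment. It does not close the gap. The analysis of covariance is exploratory, and covariates such as baseline MRI metric and type of therapeutic suit a model in patients only. Neither the subgroup work nor the correlations yield an adjusted patient-control difference.

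Second, the BMI figures are not the trial's. A reader might infer that a gap of about 3 kg/m2 is present and alone accounts for 0.084 L. The documents do not support that: they give no BMI for either group, no BMI SD and no slope. The background remark that "85% of obese people with T2D had NAFLD, detected by MRI" describes people already selected as obese, not this cohort. This objection stands, and the figures are therefore given as ranges.

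Third, if raw means differ, rejecting equality of raw means is correct, so the 13% and 61% are not false-positive rates for the stated test. That is also right; the issue is what the difference is taken to mean.

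Fourth, indexing to body surface area uses weight and may remove enlargement that accompanies fat infiltration, which the study wants to describe. This is a good reason to report an indexed value beside the raw one and not in its place.

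**Conclusion.** The point holds for the size metrics. The protocol fixes three matching factors, raw values and an unadjusted test, and specifies nothing for body size in the patient-control contrast. If patients are heavier than controls, a raw liver-volume difference could be body size in part or in whole: about 0.03 to 0.13 L for a 3 kg/m2 gap, or roughly a third to one and a half times the planned 0.084 L. This rests on the assumed correlation, BMI SD and BMI gap, none of which the documents supply. That the patients are heavier is itself an assumption.

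A reader might go further and infer that the primary cT1 result is biased. The documents do not support that. The primary objective is to describe liver fibroinflammation in type 2 diabetes against healthy people; adiposity may be part of that phenotype, so a BMI-adjusted contrast answers a different question. On the assumed figures, body size would also leave most of the UK Biobank cT1 gap in place. This is an inexpensive improvement to the secondary analyses, not a challenge to the primary one.

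**What to change.** In Section 10.2 and Table 3, pre-specify for each organ volume and for aortic diameter one patient-control difference that is either indexed to body size or adjusted for height and weight, reported with its confidence interval beside the raw difference. Name the index or the covariates in advance. State that a raw size difference will not be attributed to organ abnormality unless it persists in that analysis. Say whether the exploratory analysis of covariance is meant to include the controls.

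For liver cT1 and PDFF, keep the planned comparison unchanged and add at most one supportive BMI-adjusted estimate.

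The cost is small. Height and weight are already measured in patients; the same two values must be obtained for the controls, and the protocol does not say whether UK Biobank and the other studies will supply them. Two figures instead of one are then reported for each size metric.
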